5.1.3.2 Post therapies date imputation

Start date

Imputed date = \max (last date of study drug + 1, first day of the month), if day is missing;

Imputed date = \max (last date of study drug + 1, 01JAN), if day and month are missing.

End date: No imputation.

5.1.3.3 Other imputations

Incomplete date for death

All dates must be completed with day, month, and year.

If the day or month is missing, death will be imputed to the maximum of the last contact date (excluding the date of death) and the following:

• Missing day: 15th of the month and year of death

• Missing day and month: July 1st of the year of death

5.2 AEs coding/grading

Major gastrointestinal bleeding

Major gastrointestinal bleeding (See Section 2.8) is defined as an AE that may include one of the following MedDRA preferred terms:

Gastric haemorrhage

Gastrointestinal haemorrhage

Small intestinal haemorrhage

Oesophageal haemorrhage

Large intestinal haemorrhage

Rectal haemorrhage

Melaena

Duodenal ulcer haemorrhage

Gastric ulcer haemorrhage

Peptic ulcer haemorrhage

Large intestinal ulcer haemorrhage

Oesophageal ulcer haemorrhage

Haematochezia

Novartis For business use only Page 40 RAP M3 Amendment 4 ICL670A2302

Infections requiring intravenous antimicrobials- definition (Section 2.7.1.8)

- Infections will be determined from the reported adverse events with system organ class "Infections and infestations" and action taken "Concomitant medication taken".
- Antimicrobial therapy will be determined from the reported concomitant medications for patients who had an infection AE.
- The selection of medications will be based on the following categories of WHO low level ATC codes: D01, D04, J01, J02, J04, J05, P01, and P02.
- The route of administration must be specified as "intravenous (i.v.)".
- Contemplable events will be combined with medications (of the same patient) based on the following criteria: start date of medication ≥ start date of AE and start date of medication ≤ minimum (start date of AE + 1, end date of AE).

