#### AND

- Total bilirubin > 2 mg/dL at two consecutive visits
- 4. Liver cirrhosis confirmed by:
  - The presence of at least one of the following symptoms/signs: cirrhosis-related ascites, spontaneous bacterial peritonitis, hepatic encephalopathy, variceal bleeding due to portal hypertension

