For each treatment group, survival functions for time from randomization to the composite primary endpoint (event-free survival) will be estimated and displayed by the Kaplan-Meier method.

Sensitivity/supportive/exploratory analyses for the primary endpoint:

- Point estimate and two-sided confidence interval for an adjusted hazard ratio from a Cox proportional hazard regression model stratified for the randomization factors; adjustment for (partly data driven) demographic and/or baseline characteristics of clinical interest:
- Unadjusted hazard ratio estimates for each of the strata defined by the randomization factors;
- Analysis analog to the primary statistical analysis but patients with premature discontinuation of randomized study treatment will be censored at the day of last administration of randomized study treatment;
- Summary of the types of events observed;
- Statistical analyses based on the PPS instead of the FAS.

Statistical analysis methods for secondary efficacy endpoints:

Analyses will be described in the full clinical study protocol.

Statistical analysis methods for safety endpoints:

Following (Fleming 2008), the goal of this exploratory trial is not to determine whether there is significant evidence to rule out the null hypothesis of no increased risk.

In contrast, the objective here is to exclude levels of increased risk (for pre-specified adverse events mentioned in the Endpoints section) that would be clinically unacceptable in the context of the level of benefit that is likely to be provided by iron chelation using deferasirox in MDS patients with iron overload. Therefore, two-sided 95% confidence intervals for risk (or hazard, if applicable) ratios will be calculated. Incidences of treatment emergent (serious) adverse events (including combinations of MedDRA terms as defined by Standardized MedDRA Queries) will be summarized by treatment group. Laboratory data will be summarized using descriptive statistics and shift tables (using CTCAE classification where available) by treatment group.

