# 1.3 Safety profile

Deferasirox has demonstrated acceptable safety and tolerability in adult and pediatric patients with transfusional iron overload (Cappellini 2006), (Vichinsky 2007). The most frequent reactions reported during the first year of treatment with deferasirox in adult and pediatric patients included gastrointestinal (GI) disturbances in about 26% of patients (mainly nausea, vomiting, diarrhea, or abdominal pain), and skin rash in about 7% of patients. These reactions were dose-dependent, mostly mild to moderate, generally transient and mostly resolved even if treatment was continued. In addition, there have been rare reports of upper GI hemorrhage and/or ulceration in patients receiving deferasirox. There have been very occasional postmarketing reports of erythema multiforme, leukocytoclastic vasculitis and hypersensitivity reactions (including anaphylaxis and angioedema). Alopecia, usually comprising thinning of the hair, has been occasionally reported in patients receiving deferasirox.

Mild, non-progressive increases in serum creatinine, mostly within the normal range, occurred in about 36% of patients during the first year of treatment. These were dose-dependent, often resolved spontaneously and were sometimes alleviated by reducing the dose. Rare cases of acute renal failure, defined as a serum creatinine increases  $\geq 2 \times ULN$ , and usually reversible after treatment interruption (and sometimes a brief course of hemodialysis), have been reported following the prescription use of deferasirox.

Elevations of liver transaminases were reported as an adverse reaction in about 2% of patients. These were not dose-dependent and most of these patients had elevated levels prior to receiving deferasirox. Elevations of transaminases >10 × ULN were uncommon (0.3%). There have been postmarketing reports of hepatic failure, mostly in patients with severe baseline liver disease.

There have been reports of cytopenias, mostly in patients with pre-existing blood disorders which are frequently associated with failure of the bone marrow to produce sufficient amounts of blood cells.

High frequency hearing loss and lenticular opacities (early cataracts) have been uncommonly observed in patients treated with deferasirox.

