#### Proportion of patients with major gastrointestinal bleeding

An evaluation of the proportion of patients with major gastrointestinal bleeding will be performed. Major gastrointestinal bleeding is defined as an AE that may include one of the following MedDRA preferred terms:

Gastric haemorrhage

Gastrointestinal haemorrhage

Small intestinal haemorrhage

Oesophageal haemorrhage

Large intestinal haemorrhage

Rectal haemorrhage

Melaena

Duodenal ulcer haemorrhage

Gastric ulcer haemorrhage

Peptic ulcer haemorrhage

Large intestinal ulcer haemorrhage

Oesophageal ulcer haemorrhage

Haematochezia

Frequency tables will be prepared by treatment group. Results will also be provided for annual time intervals.

In addition, a statistical analysis of the multivariate (recurrent) major gastrointestinal bleeding data will be performed.

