2.8 Safety analyses

As stated in the protocol (Section 3.2), one of the secondary objectives was to evaluate safety, in particular to assess the levels of increased risk for pre-specified adverse events (renal dysfunction, neutropenia, thrombocytopenia, gastrointestinal bleeding, and laboratory abnormalities) that would be clinically unacceptable in the context of the level of benefit that is likely to be provided by iron chelation using deferasirox in MDS patients with iron overload.

Endpoints for the secondary safety objectives are as follows:

- 1. Proportion of patients with significant renal dysfunction
- 2. Proportion of patients with newly occurring moderate or severe neutropenia or thrombocytopenia
- 3. Proportion of patients with major gastrointestinal bleeding
- 4. Time to study drug discontinuation due to an adverse event or laboratory abnormality
- 5. Incidence of other adverse events and laboratory abnormalities

The first four endpoints are defined and evaluated as follows:

Proportion of patients with significant renal dysfunction defined as serum creatinine ≥ 2 times ULN at two consecutive assessments (at least 7 days apart) Frequency tables by treatment group will be prepared along with a two-sided 95% confidence interval for evaluation of DFX in contrast to placebo. Results will also be

Endpoint	Analysis
Proportion of patients with newly occurring neutropenia (absolute neutrophils count <1.0×10 ⁹ /L) or thrombocytopenia (platelets <50×10 ⁹ /L)	provided for annual time intervals.
Proportion of patients with major gastrointestinal bleeding.	
Time to study drug discontinuation due to an AE or laboratory abnormality, more specifically date of study drug discontinuation due to an AE or laboratory abnormality minus date of randomization plus 1.	The time-to-event analysis follows the description given in Section 2.5.2.2 The statistical test will be exploratory in nature. For the analysis of time from randomization to study drug discontinuation due to an AE or laboratory abnormality (see Section 2.8.3), patients who did not discontinue study medication due to an AE or laboratory abnormality will be censored at the date of study drug discontinuation.

Proportion of patients with moderate or severe anemia will be analyzed like newly occurring neutropenia.

Other analyses and other safety data (ocular and auditory examinations, electrocardiogram, and vital signs) will be also considered.

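### The 13-term list for major GI bleeding covers upper-GI bleeding only in part: it has no site-unspecified upper GI haemorrhage term and no haematemesis term

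*SAP*

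**What the plan says.** Both documents define the endpoint by a list of MedDRA preferred terms. SAP 5.2: "Major gastrointestinal bleeding (See Section 2.8) is defined as an AE that may include one of the following MedDRA preferred terms". Protocol 10.5.2.2: "Major gastrointestinal bleeding is defined as an AE that may include one of the following MedDRA preferred terms". The 13 terms that follow are the same in each, so the two documents do not disagree on this point. SAP section 4, which records changes to protocol-specified analyses, mentions only neutropenia and thrombocytopenia.

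The list feeds the secondary safety endpoint in SAP 2.8, "Proportion of patients with major gastrointestinal bleeding". Protocol 10.5.2.2 also plans a recurrent-event analysis of major GI bleeding.

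On known risk, Protocol 1.3 says "there have been rare reports of upper GI hemorrhage and/or ulceration in patients receiving deferasirox". On purpose, the statistical part of the protocol synopsis says that "the objective here is to exclude levels of increased risk (for pre-specified adverse events mentioned in the Endpoints section" that would be clinically unacceptable, and that "two-sided 95% confidence intervals for risk (or hazard, if applicable) ratios will be calculated". GI bleeding is one of the pre-specified events.

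**The concern.** The protocol describes the bleeding risk of this drug by a general label, upper GI hemorrhage, and no entry in the list carries that label. Vomited blood, a presenting sign of such bleeding, has no entry either, whereas the lower-tract signs rectal haemorrhage and haematochezia do. If the endpoint is programmed as a match to the list, a patient whose only bleed report is coded to an absent term counts as having no major GI bleed.

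This matters more here than in a routine AE table, because the stated aim is to exclude an unacceptable increase in risk by means of a confidence interval. Incomplete counting makes that interval less precise. If the losses fall unevenly between arms, it also shifts the estimate.

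**Working it through.** The documents give no bleeding rate, margin or power for this endpoint, so there is no planned figure to reproduce. The check has two parts.

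**1. What the list covers**

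| Group | Terms | Number |
|---|---|---|
| Upper-GI site named | gastric, oesophageal, duodenal ulcer, gastric ulcer, peptic ulcer and oesophageal ulcer haemorrhage | 6 |
| Site not named, can catch upper-GI bleeds | melaena; gastrointestinal haemorrhage | 2 |
| Other | small intestinal, large intestinal, rectal and large intestinal ulcer haemorrhage; haematochezia | 5 |
| Total | | 13 |

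A text search of the 13 terms for *upper*, for *haematemesis* or *hematemesis*, and for *varic* finds 0 matches each. Coverage of upper-GI bleeding is therefore partial: the site-specific diagnoses are in, while the general diagnosis and the vomiting-of-blood sign are out.

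**2. What a gap could do to the estimate (illustration)**

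Inputs from the documents: 210 patients randomized 2:1, so 210 × 2/3 = 140 deferasirox and 210 × 1/3 = 70 placebo; the measure is a risk ratio with a two-sided 95% interval. The true risks and the share of bleeds lost are assumptions.

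Formulas: RR = p1/p0; SE(log RR) = √[(1−p1)/(140·p1) + (1−p0)/(70·p0)]; limits = RR × exp(±1.96·SE).

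*Equal loss, true risk 10% in each arm.* With full capture, SE = √(0.9/14 + 0.9/7) = 0.439 and the upper limit is exp(1.96 × 0.439) = 2.36.

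| Share captured in both arms | RR | 95% limits |
|---|---|---|
| 100% | 1.00 | 0.42 to 2.36 |
| 90% | 1.00 | 0.40 to 2.49 |
| 75% | 1.00 | 0.37 to 2.74 |
| 50% | 1.00 | 0.29 to 3.49 |

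*Loss only in the deferasirox arm, true risks 10% vs 5%.* The 5-point excess is taken to be upper-GI bleeds, and a fraction m of it is coded to absent terms. The counted deferasirox risk is 0.05 + 0.05 × (1 − m). For m = 0.5 this is 0.075, and 0.075/0.05 = 1.50.

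| Fraction of the excess missed (m) | RR | 95% limits |
|---|---|---|
| 0 | 2.00 | 0.64 to 6.23 |
| 25% | 1.75 | 0.55 to 5.54 |
| 50% | 1.50 | 0.46 to 4.86 |
| 75% | 1.25 | 0.37 to 4.17 |
| 100% | 1.00 | 0.29 to 3.49 |

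The upper limit moves in opposite directions in the two tables: it rises under equal loss and falls under loss confined to deferasirox.

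**The case against.** The strongest reply is that the gap is narrow. Most specific upper-GI diagnoses are listed, including four upper-GI ulcer bleeds, which answers the ulceration half of the risk described in Protocol 1.3. The endpoint counts patients, so a patient is lost only if every bleed report carries an unlisted term; one report of melaena or of gastrointestinal haemorrhage is enough to count. This stands, and it rules out saying that the endpoint cannot see upper-GI bleeding. It does not help the recurrent-event analysis in the same way, because there each unlisted event is lost.

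Second, the wording *may include* does not say that the list is closed. That is correct, but it is no defence. If the list is closed, the events above are lost. If it is open, the endpoint can be completed after the data are seen.

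Third, nothing disappears from the report. SAP 2.8.1 tabulates all treatment-emergent AEs by system organ class and preferred term, and SAP 2.8.1.1 adds groupings of special interest. This stands as far as visibility goes. The groupings are defined in a separate document that may be updated during the trial, so one for GI bleeding can be neither confirmed nor ruled out, and neither source feeds this endpoint or its interval.

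Fourth, with 140 vs 70 patients the interval is wide in any case. This is also true: in the 10% vs 5% illustration, neither 6.23 nor 4.86 would exclude a fourfold risk. It limits the practical effect but is no reason to leave a correctable gap.

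Two further inferences are tempting and should not be drawn. The protocol synopsis mentions AE summaries "including combinations of MedDRA terms as defined by Standardized MedDRA Queries"; a reader might take this as a commitment to a GI-haemorrhage query for this endpoint, but the text is general and names no such query. Variceal bleeding is also absent from the list, but the protocol uses "variceal bleeding due to portal hypertension" as a sign of cirrhosis in the primary composite and does not present it as the bleeding harm this endpoint targets. Whether to add it is a matter of judgement.

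**Conclusion.** The point holds as a definition gap shared by both documents. The list covers upper-GI bleeding in part and omits the general upper GI haemorrhage label and haematemesis, and its wording leaves open whether it is exhaustive.

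That patients would be missed rests on one assumption that the documents cannot confirm: that such reports code to their own preferred terms and that the patient has no other listed bleed.

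A reader might infer that the endpoint is biased in favour of deferasirox. The documents do not support this. It would require losses concentrated in the deferasirox arm, and Protocol 1.3 offers only rare reports, with no split by type of bleed and no comparison with placebo. Equal loss leaves the risk ratio unchanged and raises the upper limit, which is the less favourable direction for the drug. The size and direction of the effect are unknown, and the tables show only what each pattern would do under assumed risks. The correction is worth making because the endpoint is a pre-specified harm and the change is cheap.

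**What to change.** Before unblinding, amend SAP 5.2 as follows:

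- State that the list is exhaustive, replacing the permissive wording.
- Add at least upper gastrointestinal haemorrhage and haematemesis. Consider lower gastrointestinal and variceal haemorrhage, or replace the list with a named and versioned standard MedDRA query.
- Keep the present 13 terms as a sensitivity table, so that the result under the protocol definition remains available.
- Record the departure from Protocol 10.5.2.2 in SAP section 4, as was done for neutropenia and thrombocytopenia.

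The cost is SAP wording, one lookup table and one extra output, with no new data collection. The downside is a small, documented departure from the list defined in the protocol.

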## 7.5.1 Adverse events

An adverse event for the purposes of this protocol is the appearance of (or worsening of any pre-existing) undesirable sign(s), symptom(s), or medical condition(s) occurring after signing the informed consent even if the event is not considered to be related to the study drug(s). However, it must be noted that MDS is not considered an adverse event. MDS is a required condition for study entry and is expected to be reported as Medical History for all patients. Time to disease progression is a secondary efficacy endpoint. Please refer to Section 6.1 for the protocol-specific definitions of study drug and study treatment.

Adverse events (but not serious adverse events) occurring before starting study treatment but after signing the informed consent form are recorded on the Medical History/Current Medical Conditions eCRF. Abnormal laboratory values or test results that induce clinical signs or symptoms, are considered clinically significant, require therapy (e.g., any hematological abnormality that requires transfusion or cytokine treatment), or interruption of study medication should be recorded on the Adverse Events eCRF under the signs, symptoms or diagnosis associated with them. Abnormal Laboratory values that do not meet this criteria are not reported as Adverse Events. SAEs occurring after signing the Informed Consent are recorded on the Adverse Event eCRF.

The occurrence of adverse events should be sought by non-directive questioning of the patient at each visit during the study. Adverse events also may be detected when they are volunteered by the patient during or between visits or through physical examination, laboratory test, or other assessments. As far as possible, each adverse event should be evaluated to determine:

- 1. The severity grade (mild, moderate, severe)
- 2. Its relationship to deferasirox (suspected/not suspected)

- 3. Its duration (start and end dates or if continuing at final examination)
- 4. Action taken (no action taken; study drug dosage adjusted/temporarily interrupted; study drug permanently discontinued due to this adverse event; concomitant medication taken; non-drug therapy given; hospitalization/prolonged hospitalization)
- 5. Whether it is serious, where a serious adverse event (SAE) is defined as one which:
  - Is fatal or life-threatening
  - Results in persistent or significant disability/incapacity
  - Constitutes a congenital anomaly/birth defect

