2.8.1 Adverse events (AEs)

All AEs recorded during the study are coded using the latest version of the medical dictionary for regulatory activities (MedDRA) and summarized by treatment group and overall. Adverse events are not assessed according to the common terminology criteria for AEs (CTCAE); instead, AE severity (mild, moderate, severe) is used to report treatment-emergent AEs starting on or after the date of first study medication (including AEs that start within 28 days after the discontinuation of the study medication).

Frequency tables for treatment-emergent AEs will be presented, for each treatment group, the number of patients, and the percentage of patients experiencing the AE. Multiple occurrences of the same event in the same patient will be counted only once in the frequency tables. However, all adverse events will be included in the AE listings.

Frequency tables will display at least the MedDRA system organ class and preferred term, AE severity (mild, moderate, severe), and relationship to study drug. The following tables will be generated:

• Adverse events, regardless of study drug relationship

- Serious adverse events, regardless of study drug relationship
- Serious adverse events, suspected to be study drug relationship
- Adverse events leading to study drug discontinuation, regardless of study drug relationship
- Adverse events requiring dose adjustment or interruption, regardless of study drug relationship
- Adverse events requiring additional therapy, regardless of study drug relationship
- Adverse events, suspected to be study drug related
- Adverse events which are not serious adverse events, regardless of study drug relationship

For the requirements of ClinicalTrials.gov and EudraCT, two required tables on <ontreatment/treatment emergent> adverse events which are not serious adverse events with an incidence greater than 5% and on <on-treatment/treatment emergent> serious adverse events and SAE suspected to be related to study treatment will be provided by system organ class and preferred term on the safety set population.

If for a same patient, several consecutive AEs (irrespective of study treatment causality, seriousness and severity) occurred with the same SOC and PT:

- a single occurrence will be counted if there is ≤ 1 day gap between the end date of the preceding AE and the start date of the consecutive AE

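### Major GI bleeding has no severity or seriousness criterion; if minor bleeds are less treatment-related, they pull the safety risk ratio toward 1

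*SAP*

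**What the plan says.** Protocol Section 10.5.2.2 states: "Major gastrointestinal bleeding is defined as an AE that may include one of the following MedDRA preferred terms". SAP Section 5.2 repeats the wording, so that major bleeding "is defined as an AE that may include one of the following MedDRA preferred terms", and gives the same 13 terms. They range from ulcer haemorrhages to "Rectal haemorrhage" and "Haematochezia". Neither text, nor the endpoint table in SAP Section 2.8, asks for a severity grade, seriousness, a haemoglobin fall, transfusion or hospital admission.

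The neighbouring safety endpoints do carry thresholds. Renal dysfunction needs creatinine of at least twice the ULN at two consecutive assessments. Neutropenia and thrombocytopenia have numeric cut-offs in SAP Section 2.8.

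Protocol Section 7.5.1 has both severity and seriousness assessed for each adverse event. For the general tables, SAP Section 2.8.1 says: "Frequency tables will display at least the MedDRA system organ class and preferred term, AE severity (mild, moderate, severe), and relationship to study drug". A separate serious-event table is also listed.

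For this endpoint SAP Section 2.8 plans frequency tables, a two-sided 95% interval and annual results. The protocol also promises that "a statistical analysis of the multivariate (recurrent) major gastrointestinal bleeding data will be performed".

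**The concern.** The endpoint's name implies clinically important bleeding, but the rule admits any bleed coded to a listed term. The purpose of the contrast makes this matter. The protocol synopsis says the safety analysis is not looking for a significant difference. It aims to rule out increases in risk that would be unacceptable given the likely benefit, and it names risk ratios (or hazard ratios where applicable) with 95% intervals as the tool.

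For that purpose, an error toward a ratio of 1 is the unsafe direction. Background minor bleeding that occurs equally in both arms adds the same amount to numerator and denominator. The ratio shrinks, the interval narrows because there are more events, and the upper limit drops. A real excess of major bleeding could then appear to be excluded.

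**Working it through.** **Nothing to reproduce.** The documents give no bleeding rate by arm or severity, no margin and no power for this endpoint. Protocol Section 10.8 says power was not calculated for secondary variables. The figures below are an illustration on assumed rates.

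**Inputs**
- Sample size 210, randomised 2:1 (protocol Section 10.7, SAP Section 3): 210 × 2/3 = 140 deferasirox, 210/3 = 70 placebo.
- Assumed major bleeds: 3% placebo and 6% deferasirox (true ratio 2). Second case: 3% and 9% (true ratio 3).
- Assumed minor bleeds: 0% to 15% on placebo, independent of major bleeds within a patient.

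**Formulas**
- Risk of any listed bleed in an arm: p = 1 − (1 − major)(1 − minor).
- RR = pD/pP; SE(log RR) = √[(1 − pD)/(140 pD) + (1 − pP)/(70 pP)]; 95% CI = RR × exp(±1.96 SE).

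Major bleeds only: SE = √(0.94/8.4 + 0.97/2.1) = 0.757, so RR 2.00, CI 0.45 to 8.83.

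**Case A: minor bleeds unrelated to treatment (same rate in both arms).** The risk difference is 0.03 × (1 − minor).

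| Minor, both arms | Placebo | Deferasirox | RR | 95% CI | Difference (points) |
|---|---|---|---|---|---|
| 0% | 3.00% | 6.00% | 2.00 | 0.45–8.83 | 3.00 |
| 3% | 5.91% | 8.82% | 1.49 | 0.51–4.38 | 2.91 |
| 5% | 7.85% | 10.70% | 1.36 | 0.54–3.47 | 2.85 |
| 10% | 12.70% | 15.40% | 1.21 | 0.59–2.51 | 2.70 |
| 15% | 17.55% | 20.10% | 1.15 | 0.62–2.10 | 2.55 |

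With a true major ratio of 3 (CI 0.72 to 12.57 on major bleeds alone), 10% minor bleeds give RR 1.43 (0.70 to 2.89) and 15% give 1.29 (0.71 to 2.33). Both upper limits lie below the true ratio for major bleeding.

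**Case B: minor bleeds carry the same ratio of 2.**

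| Minor, placebo / deferasirox | Placebo | Deferasirox | RR | 95% CI |
|---|---|---|---|---|
| 3% / 6% | 5.91% | 11.64% | 1.97 | 0.70–5.57 |
| 15% / 30% | 17.55% | 34.20% | 1.95 | 1.12–3.40 |

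Here the ratio hardly moves, and the narrower interval is a genuine gain in precision.

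**Recurrent analysis.** Protocol Section 10.5.2.2 promises it. SAP Section 2.8 does not mention it and gives no model. SAP Section 4 declares one change only, the redefinition of neutropenia and thrombocytopenia. SAP Section 2.1 says in general terms that data are analysed according to protocol Section 10.

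**The case against.** - **The two documents agree.** The SAP copies the protocol's definition, so there is no contradiction. This stands: the point concerns the choice of definition.
- **Dilution is conditional.** It needs minor bleeds to be less treatment-related than major ones. In Case B the broad count is better: the computed power to detect a difference rises from 13% to between 24% and 73%. This stands. The documents offer only hints. Protocol Section 1.3 describes rare upper GI haemorrhage, whereas several listed terms are lower GI. Protocol Section 6.7.4.1 warns of GI irritation and bleeding in general, with ulcerogenic drugs or anticoagulants.
- **It depends on the scale.** In Case A the risk difference only moves from 3.00 to 2.55 points. SAP Section 2.8 does not name the scale of its interval, and the only two-group interval for proportions that the SAP defines (Section 5.5.3) is for a difference. This limits the point but does not remove it, because the protocol synopsis names ratios.
- **General tables already show severity and serious events.** This helps in part. Rows by preferred term cannot be added to give a patient-level proportion, since one patient may have several terms, and no interval is planned for the severe or serious subset.
- **Redefining the endpoint would leave few events.** At 3% and 6% one expects about 2 and 8 patients (70 × 0.03 = 2.1; 140 × 0.06 = 8.4). This is a good reason to add a row and keep the planned count.

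**Conclusion.** The endpoint called major GI bleeding has no criterion that makes a bleed major. That follows from the text alone. The consequence is conditional: if minor bleeds are less treatment-related, a true ratio of 2.00 would appear as 1.49 to 1.15 with 3% to 15% minor bleeds in both arms, and the upper limit would fall from 8.83 to between 4.38 and 2.10. If they share the drug effect, the ratio stays at 1.95 to 1.97. All these rates are assumptions, and the loss is on the ratio scale.

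A reader might infer that minor bleeds do dilute the contrast in this trial. The documents do not support that, because they give no bleeding rates by severity or arm. A reader might also infer that the SAP cancelled the recurrent-event analysis. It is silent on it, and its general reference to protocol Section 10 still reaches it, so the defect is an unspecified analysis whose status is unclear. The point is a cheap improvement and does not invalidate the safety analysis.

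**What to change.** 1. Keep the planned any-severity count as the protocol-defined endpoint, and label it in the output as any listed GI bleed. In SAP Section 5.2, state whether the term list is closed, since the present wording leaves that open.
2. In SAP Section 2.8, add one pooled patient-level row restricted to listed events that are serious or graded severe, with the same two-sided 95% interval.
3. Either specify the recurrent GI-bleeding analysis in SAP Section 2.8 or declare its removal, with a reason, in SAP Section 4.

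The cost is a few lines of SAP text and one extra table row, using data already collected. If the recurrent analysis is kept, its model must also be written down. The drawback is that the added row will have few events and a wide interval, so it may exclude little. That shows fairly how much the trial can say about major bleeding.
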